6.9.6 Expectedness

- AEs or ARs are considered “unexpected” if they **are not** listed in the Reference Safety Information section of the Investigator’s Brochure for AR-15512 or **are not** listed at the specificity or severity that has been observed. “Unexpected,” as used in this definition, also refers to AEs or ARs that **are** mentioned in the Investigator’s Brochure as occurring with this class of drugs or as anticipated from the pharmacological properties of AR-15512 and **are not** specifically mentioned as occurring with the study drug.

For example, under this definition, hepatic necrosis would be unexpected (by virtue of greater severity) if the Investigator’s Brochure referred only to elevated hepatic enzymes or hepatitis. Similarly, cerebral thromboembolism and cerebral vasculitis would be unexpected (by virtue of greater specificity) if the Investigator’s Brochure listed only cerebral vascular accidents. “Unexpected,” as used in this definition, also refers to AEs or ARs that are mentioned in the Investigator’s Brochure as occurring with a class of drugs or as anticipated from the pharmacological properties of the drug but are not specifically mentioned as occurring with the particular drug under investigation.

- An Investigator must immediately (i.e., within 24 hours from time of awareness) report any SAE or SAR (see Section 6.9.2 for definitions) to the Sponsor or its clinical research organization (CRO) representative, whether or not considered drug-related, including those listed in the protocol or Investigator’s Brochure.

6.9.7 Clinical Laboratory Adverse Events

Clinical laboratory values (other than pregnancy tests results) that are noted as abnormal and clinically significant at study exit and that are changes from Screening values will be documented as AEs.

6.9.8 Serious Adverse Events, Serious Adverse Reactions or Suspected Unexpected Serious Adverse Reactions

6.9.8.1 Reporting SAEs or SARs

An Investigator must immediately (i.e., within 24 hours) report any SAE or SAR (see Section 6.9.2 for definitions) to the Sponsor or its CRO representative, whether or not considered study intervention-related, including those listed in the protocol or Investigator's Brochure. The Investigator must use the SAE report form and include an assessment of whether there is a reasonable possibility that the drug caused the event. The Investigator must report any SAE or SAR that occurs or is observed during the study. In case of incomplete information, the Investigator must provide follow-up information as soon as possible, again using the SAE report form. The email or fax to submit the SAE report is found in Section 6.9.8.3.

SAE reports will be evaluated by the Medical Monitor. Regulatory authorities, IRB, and Investigators at each of the study sites will be informed as required.

6.9.8.2 Reporting Suspected Unexpected Serious Adverse Reactions (SUSARs)

The Investigator must immediately (i.e., within 24 hours) report SUSARs. In the event of SUSAR, the site must notify the Medical Monitor (Section 10.2) for the study and submit an SAE report form within 24 hours of notification, observation, or occurrence of the SUSAR, whether or not complete information is available. In the case of incomplete information, the Investigator must provide follow-up information as soon as possible using the SAE report form.

6.10 Participant Discontinuation/Withdrawal from the Study

A subject may exit the study by their own volition or at the discretion of the Investigator or the Medical Monitor. Any subject may decide to voluntarily withdraw from the study at any time without prejudice.

The subject may also be discontinued from the study for the following reasons:

- AEs (AEs including, in the opinion of the Investigator, clinically relevant laboratory abnormalities, and intercurrent diseases reported by the subject or observed by the Investigator with documentation on the eCRF)
- Withdrawal of Consent
- Non-compliance (e.g., non-adherence to scheduled follow-up visits or use of study intervention)

- Lost to Follow-up
- Disallowed Concurrent Treatment
- Investigator Decision
- Protocol Deviation
- Death
- Does not meet entry criteria
- Other

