5.6 Study Intervention Compliance

At the Screening visit, the morning dose will be administered in clinic by the subject under supervision from site personnel. For the Day 1, Day 7, Day 14, Day 28 and Day 90 visits, the "evening" dose will be administered by designated site personnel; all other doses will be administered by the subject. Study intervention compliance will be assessed by site records for these treatments.

The subjects' used and unused study intervention vials will be collected at each visit from the Baseline visit up to and including the Day 90 (Exit) visit to assess dosing compliance. Dosing compliance will be based off the used and unused vial count. If the subject is less than 80% or more than 125% compliant with dosing based on the expected number of used and unused vials, then the subject will be deemed non-compliant and a protocol deviation must be recorded. Subjects will be instructed on instillation and storage of study intervention at the end of each visit (excluding the exit visit), as well as provided written instructions.

These guidelines will be used by the Investigator for determining the subject's necessary compliance for the study and for recording deviations from this compliance.

The study centers will keep an accurate accountability record that specifies the amount of study intervention dispensed to each subject, the amount of study intervention returned to the site, and the dates of each.

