6.8.5 Dilated Fundoscopy

Dilated fundus exams will be performed in both eyes using indirect ophthalmoscopy. The Investigator will make observations of the vitreous, retina, macula, choroid and optic nerve.

Observations will be graded as Normal or Abnormal. Abnormal findings that are clinically significant (as determined by the Investigator that may interfere with study parameters or otherwise confound the data) and those that are not clinically significant will be described. An indirect Fundoscopy examination should be performed if retinal disease is detected.

- Vitreous: Examination should emphasize the visual axis.
- Retina, Macula, Choroid: Include an observation of the retina and its blood vessels. Eyes should be excluded from the study if active inflammation is present.
- Optic Nerve: Significant damage or cupping to the optic nerve should be noted.

It is recommended that tropicamide 1% ophthalmic solution be used to dilate subjects.

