2.3 Estimands

2.3.1 ESTIMAND 1 (PRIMARY ESTIMAND)

The primary comparison will be based on the ITT population targeting the treatment effect attributable to the randomly assigned treatment, regardless of compliance to study treatment and assuming subjects who discontinued due to lack of efficacy, AEs, or disallowed concurrent treatments follow the behavior of subjects in the reference arm for the duration of the study and subjects who discontinued for other reasons

(outside of lack of efficacy, AEs or use of disallowed treatment) would follow the behavior of subjects who are still in the study under same randomly assigned treatment.

[figure not shown]
- Population: subjects in the ITT population with DED defined through enrollment criteria
- Endpoint:
 - Proportion of subjects with ≥ 10 mm increase in unanesthetized Schirmer score on Day 14
- Intercurrent event:
 - Non-optimal treatment compliance is ignored. [treatment policy strategy]
 - Withdrawal due to lack of efficacy, AEs, or disallowed concurrent treatment - multiple imputations using vehicle treatment group regardless of randomized treatment group is used to impute missing data. [hypothetical strategy, missing not at random]
 - Withdrawal due to reasons other than lack of efficacy, AEs, or disallowed concurrent treatment - multiple imputations using randomized treatment is used to impute missing data. [hypothetical strategy, missing at random]
- Population-level summary:
 - Difference in the proportion of subjects with ≥ 10 mm increase in unanesthetized Schirmer score on Day 14 between AR-15512 (0.003%) and vehicle

3. Study Design and Procedures

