7.1 Intent-to-Treat

The Intent-to-Treat (ITT) population includes all randomized subjects. The primary efficacy analysis will be performed on the ITT population. Subjects in the ITT will be analyzed as randomized.

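### Protocol 6.10 lets a site exit a randomized subject for non-compliance that SAP Estimand 1 says to ignore, so an observable outcome goes uncollected and is imputed

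*Protocol*

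**What the plan says.** **Exit from the study.** Protocol 6.10 states: "The subject may also be discontinued from the study for the following reasons". Its grounds include "Non-compliance (e.g., non-adherence to scheduled follow-up visits or use of study intervention", "Protocol Deviation", investigator decision and "Does not meet entry criteria". Protocol 5.6 classes a subject who is "less than 80% or more than 125% compliant with dosing" as non-compliant and requires a deviation to be recorded, so under-dosing can meet two of the grounds at once.

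**After exit.** Protocol 6.10.1 asks for a final visit with the Early Termination examinations when a subject withdraws consent or is discontinued for non-compliance. The list in Protocol 7.3 contains no Schirmer test, SANDE or VAS. In both visit schedules (Protocol Appendix 1 and SAP Table 1) those rows are visible and blank in the Early Termination column. SAP 8.5 sends Early Termination data to listings only.

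**Estimand.** SAP 2.3.1 states: "Non-optimal treatment compliance is ignored. [treatment policy strategy". It handles withdrawals in two branches, both labelled hypothetical. Withdrawals for lack of efficacy, an adverse event or a prohibited therapy are imputed from the vehicle arm. All other withdrawals are imputed from the randomized arm under missing at random (MAR). SAP section 1 says that its methods supersede those of the protocol.

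**Analysis set.** SAP 7.1 states: "The Intent-to-Treat (ITT) population includes all randomized subjects".

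**The concern.** Treatment policy for non-compliance means that the outcome counts whatever the dosing was, so the outcome has to be measured. Protocol 6.10 lets the site end that measurement because of the very event the estimand says to ignore.

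An under-dosing subject who is kept contributes an observed value. The same subject, if exited, contributes a value modelled on those who stayed in the same arm. The choice is discretionary and no criterion is given, so practice may differ between sites. Under-dosing may also depend on how the drop feels, so the loss need not be equal between arms.

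Exits for protocol deviation or investigator decision raise a smaller issue. Imputing them follows Estimand 1's own withdrawal rule, and the cost is avoidable loss of data.

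**Working it through.** **1. The plan's own figures (Protocol 9.7, SAP section 5).** Inputs: 202 per arm; 80% vs 30% responders; SANDE difference -7.9, SD 17.72; two-sided alpha 0.05; 10% dropout; 460 randomized.
- SANDE: 7.9 / (17.72 × √(2/202)) = 7.9 / 1.763 = 4.48. Power = Φ(4.48 - 1.96) = 0.994.
- Schirmer responders: power above 0.999.
- Sample size: 202 / 0.90 = 224.4, so 225 per arm or 450 in total, against 460 planned. 460 × 0.90 = 414, as stated.

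The stated 99% power is reproduced in both cases.

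**2. What happens to an under-dosing subject.**

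| | Kept in the study | Exited under 6.10 |
|---|---|---|
| Later efficacy visits | as scheduled | none |
| Final visit | Day 90, with Schirmer, SANDE, VAS | Early Termination, none of these |
| Rule in SAP 2.3.1 | treatment policy | hypothetical, MAR from own arm |
| Value analysed | observed | imputed |

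**3. Which endpoints are exposed.** Protocol 7.2.2 and both schedules show no vial collection at Day 7, although Protocol 5.6 speaks of each visit. Randomized vials are first returned at Day 14, the visit of the primary measurement. Removal for counted under-dosing therefore falls mostly after the primary. SAP 2.1.2 lists 11 secondary endpoints: 1 at Day 28 (SANDE), 7 at Day 90, 1 at Day 14 and 2 at Day 1. So 1 + 7 = 8 of 11 lie after Day 14. The primary is exposed only to exits before its measurement, for example after missed visits or by investigator decision.

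**4. Size.** Let d be the share of the active arm removed before the endpoint. The documents give no such rate, so d is an assumption. Suppose the removed subjects would have responded at the vehicle rate:
- treatment-policy difference = 0.80(1 - d) + 0.30d - 0.30 = 0.50 - 0.50d
- own-arm imputation targets 0.80 - 0.30 = 0.50
- overstatement = 0.50d; for SANDE, 7.9d

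| d | Subjects of 230 | Responder difference overstated (points) | SANDE overstated (points) |
|---|---|---|---|
| 1% | 2.3 | 0.5 | 0.08 |
| 2% | 4.6 | 1.0 | 0.16 |
| 5% | 11.5 | 2.5 | 0.40 |
| 10% | 23 | 5.0 | 0.79 |

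The 10% row takes the whole planned dropout and is a ceiling. For the primary it would also need every exit to fall before Day 14. If all removed active-arm subjects would have been non-responders, the responder figure is 0.80d: 0.8 points at 1% and 8.0 at 10%.

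**5. Direction.** Let q be the true response rate of removed subjects, with subscripts A (active) and V (vehicle). The bias in the difference is d_A(0.80 - q_A) - d_V(0.30 - q_V). It is zero if removed subjects would respond like their own arm. It goes against the drug if, say, only vehicle subjects are removed and q_V is below 0.30: with d_V = 5% and q_V = 0 it is -0.05 × 0.30 = -1.5 points.

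**6. Power if these subjects are kept and measured (230 per arm).** Schirmer power stays above 0.999. SANDE power is 0.997 at d = 1% and 0.990 at d = 10%, where the effect is diluted to -7.9 × 0.90 = -7.11.

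**The case against.** The strongest reply is that the plan does not make removal routine. Protocol 6.10 is permissive, Protocol 5.6 requires only a recorded deviation, SAP 12.1 tabulates the non-compliant categories, and the per-protocol set deals with significant deviators separately. The primary follows a drop given in the clinic by site staff. An under-dosing active-arm subject who attends Day 14 has just received active drug and may respond near the active rate, so the primary bias may be close to zero. All of this stands and limits the size. It does not settle which rule applies when a site does use its discretion.

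Protocol 9.4 also lists robustness analyses, including missing as failure and not-at-random imputation. The SAP supersedes the protocol's methods, and the public SAP has gaps around its efficacy sections, so their absence cannot be inferred. Such analyses probe missing data but do not recover it.

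A reader might infer more than the documents support:
- *That the intent-to-treat definition is breached.* It is not. An exited subject stays in that set, as randomized, with an imputed value.
- *That imputing deviation or ineligibility exits contradicts the estimand.* The treatment-policy rule names only compliance. Other withdrawals have their own stated rule.
- *That randomized subjects found ineligible will be removed.* Protocol 6.10 does not tie "Does not meet entry criteria" to randomized subjects. The disposition reasons in SAP section 9 omit it, and it may refer to run-in subjects who fail to requalify. Protocol 4.4 already calls those screen failures, so the entry is ambiguous.
- *That the fundus-exam sentence, "Eyes should be excluded from the study if active inflammation is present", is another post-randomization exclusion.* The exam is also done at Screening, where the sentence fits naturally, and it serves safety.
- *That the bias always favours the drug.* Step 5 of the working shows that it need not.

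**Conclusion.** The point holds for non-compliance. Protocol 6.10, 6.10.1 and 7.3 do not fit the treatment-policy rule in SAP 2.3.1, because a site can turn an event to be ignored into a withdrawal imputed under MAR. For deviation and investigator-decision exits the point is avoidable loss of outcomes, with no contradiction of the estimand.

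Per 1% of the active arm removed, the overstatement is up to 0.08 SANDE points at Day 28 and, for exits before Day 14, up to 0.5 percentage points on an assumed 50-point primary difference. Both figures assume vehicle-like outcomes in the removed subjects and imputation at the level of their own arm. If the imputation model uses earlier visits, part of the gap may be recovered; the public SAP text does not show that model. The matter is what is estimated, chiefly at Day 28 and Day 90. It is a cheap improvement and does not threaten the trial's conclusion on the primary endpoint.

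**What to change.** Reconcile Protocol 6.10, 6.10.1 and 7.3 with SAP 2.3.1:
- Separate stopping study intervention from leaving the study, with a reason recorded for each.
- State that, after randomization, non-compliance and protocol deviation are not in themselves reasons to end efficacy follow-up.
- Keep the scheduled SANDE and VAS assessments for these subjects, and the Schirmer tests wherever the in-office dose is still given, unless the subject withdraws consent.
- State that the entry on not meeting entry criteria applies before randomization.
- Use the retained data as observed under the treatment-policy rule.

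Whether intervention continues remains a medical decision, and the inflammation sentence in Protocol 6.8.5 is left as it is.

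The cost is wording in two documents and a few visits, already in the schedule, for subjects who would otherwise have been exited.

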6.10.1 Actions after Discontinuation

Also see Early Termination Procedures (Section [7.3](#)).

All subjects who discontinue study intervention due to a report of an AE must be followed and provided appropriate medical care until their signs and symptoms have remitted or stabilized or until clinically meaningful abnormal laboratory findings have returned to acceptable or pre-study limits.

For subjects who choose to withdraw consent or who are discontinued for non-compliance prior to completing the study, every possible effort should be made by the Investigator to assure there is a final visit that includes all examinations listed for the Early Termination Visit.

6.10.2 Discontinuation of the Entire Study

The entire study may be discontinued at any given site by the Investigator or the Sponsor or Sponsor representative, or at all sites by the Sponsor. Prompt, written notice of reasonable cause to all other relevant parties (Sponsor or Investigator) is required. Prompt notice to the IRB and to regulatory authorities is also required.

6.10.3 Completed Study

The study is completed when the last visit of the last subject has been completed at the last site taking part in the study. The Sponsor or Sponsor representative will be in communication with the investigational sites regarding enrollment completion.

[figure not shown]
7. STUDY ACTIVITIES

7.1 Screening and Run-In Period

7.1.1 Screening Visit (Day -14 [+3* days])

- Informed consent
- Demographics
- Medical, ophthalmic, and surgical history

- Prior or concomitant medication review
- Vital signs (heart rate and blood pressure)
- Urine pregnancy test (WOCBP only)
- Symptom Questionnaire (VAS) (Ocular Discomfort, Eye Dryness [REDACTED])
- SANDE Questionnaire (VAS)
- Corrected visual acuity
- Slit-lamp biomicroscopy
- At least 5-minute rest period

- CAE exposure

[figure not shown]
- Inclusion and exclusion criteriaAE Review
- Dispensing of the study intervention
- In office administration of study intervention by subject under site staff supervision
- Intraocular pressure
- Dilated fundus exam

* The Baseline visit is requested to be scheduled between 11 and 14 days after the Screening visit. If absolutely necessary, the Baseline visit may be delayed up to 7 days (extending the run-in period to a maximum of 21 days).

[figure not shown]
7.2 Randomized Intervention Period

7.2.1 Baseline (Day 1) Procedures

- Collection of used and unused study intervention
- Concomitant medication review
- AE review
- Vital signs (heart rate and blood pressure)
- Urine pregnancy test (WOCBP only)
- Symptom Questionnaire (VAS) (Ocular Discomfort, Eye Dryness [REDACTED])
- SANDE Questionnaire (VAS)

- Corrected visual acuity
- Slit-lamp biomicroscopy

[figure not shown]

- Inclusion and exclusion criteria review

[figure not shown]
- Randomization
- Dispensing of study intervention
- At least 30 and up to 45-minute rest period
- Pre-drop unanesthetized Schirmer test
- At least 15 and up to 20-minute rest period
- In office administration of study intervention by site staff
- Post-drop unanesthetized Schirmer test
- Hematology, chemistry, and urinalysis
- Intraocular pressure
- Dilated fundus exam

7.2.2 Day 7 (\pm 2 days) Procedures

- Concomitant medication review
- AE review
- Symptom Questionnaire (VAS) (Ocular Discomfort, Eye Dryness [REDACTED])
- SANDE Questionnaire (VAS)

- Corrected visual acuity
- Slit-lamp biomicroscopy

- Pre-drop unanesthetized Schirmer test
- At least 15 and up to 20-minute rest period
- In office administration of study intervention by site staff
- Post-drop unanesthetized Schirmer test

7.2.3 Day 14 (\pm 2 days) Procedures

- Collection of used and unused study intervention
- Concomitant medication review
- AE review
- Symptom Questionnaire (VAS) (Ocular Discomfort, Eye Dryness [REDACTED])
- SANDE Questionnaire (VAS)

[figure not shown]
- Corrected visual acuity
- Slit-lamp biomicroscopy

- Dispensing of study intervention
- At least 30 and up to 45-minute rest period

- Pre-drop unanesthetized Schirmer test
- At least 15 and up to 20-minute rest period
- In office administration of study intervention by site staff
- Post-drop unanesthetized Schirmer test

[figure not shown]
7.2.4 Day 28 (\pm 2 days) Procedures

- Collection of used and unused study intervention
- Concomitant medication review
- AE review
- Symptom Questionnaire (VAS) (Ocular Discomfort, Eye Dryness [REDACTED])
- SANDE Questionnaire (VAS)

- Corrected visual acuity

- Slit-lamp biomicroscopy

- Dispensing of study intervention
- At least 30 and up to 45-minute rest period
- Pre-drop unanesthetized Schirmer test
- At least 15 and up to 20-minute rest period

[figure not shown]
- In office administration of study intervention by site staff
- Post-drop unanesthetized Schirmer

7.2.5 Day 60 (\pm 5 days) Procedures

- Collection of used and unused study intervention
- Dispensing of study intervention

7.2.6 Day 90 (-2 / +5 days) Procedures

- Collection of used and unused study intervention
- Concomitant medication review
- AE review
- Vital signs (heart rate and blood pressure)
- Urine Pregnancy test (WOCBP only)
- Symptom Questionnaire (VAS) (Ocular Discomfort, Eye Dryness [REDACTED])
- SANDE Questionnaire (VAS)

- Corrected visual acuity
- Slit-lamp biomicroscopy

- Pre-drop unanesthetized Schirmer test
- At least 15 and up to 20-minute rest period
- In office administration of study intervention by site staff
- Post-drop unanesthetized Schirmer test
- Hematology, chemistry, and urinalysis
- Intraocular pressure
- Dilated fundus exam
- Study Exit

7.3 Early Termination Procedures

Every effort should be made to perform the following procedures at the Early Termination visit.

- Collection of used and unused study intervention
- Concomitant medication review
- AE review
- Vital signs (heart rate and blood pressure)
- Urine pregnancy test (WOCBP only)
- Corrected visual acuity
- Slit-lamp biomicroscopy
- Hematology, chemistry, and urinalysis
- Intraocular Pressure
- Dilated Fundus Exam
- Study Exit

7.4 Unscheduled Visits

An unscheduled visit may be any visit to the Investigator other than the visits specified in the protocol as possibly required for the subject's ophthalmic condition.

The investigator will perform all procedures necessary to evaluate the study participant at these visits and record any AEs in the eCRF.

